Surrogate biomarkers – In clinical practice, surrogate biomarkers may be used as alternatives to measures such as survival or irreversible morbidity. Surrogate biomarkers are measures that are reasonably likely, based on epidemiologic, therapeutic, pathophysiologic, or other evidence, to predict clinical benefit. Examples include: i) LDL level as a surrogate for risk of cardiovascular diseases in patients taking lipid-lowering agents such as atorvastatin calcium (Lipitor®); ii) blood glucose as a surrogate for clinical outcomes in patients taking anti-diabetic agents, and iii) HIV plasma viral load and CD4 cell counts as sur-

rogates for time-to-clinical-events and overall survival in patients receiving antiretroviral therapy for HIV disease.

Prognostic biomarkers – Biomarkers can also help predict clinical outcomes independent of any treatment modality. Examples of prognostic biomarkers used in clinical practice include: i) CellSearch™ to predict progression-free survival in breast cancer, ii) anti-CCP (cyclic citrullinated protein) for the severity of rheumatoid arthritis, iii) estrogen receptor status for breast cancer, and iv) anti-dsDNA for the severity of systemic lupus erythematosus.

6. Biomarker Samples from Clinical Trials: An Invaluable Resource

Adequate sample sizes and high-quality data from controlled clinical trials are key to advancements in biomarker research. Samples collected in clinical trials create the opportunity for investigation of biomarkers related to specific drugs, drug classes, and disease areas. Clinical drug development programs are therefore an invaluable resource and a unique opportunity for highly productive biomarker research. In addition to conducting independent research, pharmaceutical companies are increasingly contributing to consortia efforts by pooling samples, data, and expertise in an effort to conduct rigorous and efficient biomarker research and to maximize the probability of success.²⁶⁻²⁷

7. Informed Consent for Collection & Banking of Biomarker Samples

Collection of biological samples in clinical trials must be undertaken with voluntary informed consent of the participant (or legally-acceptable representative). Policies

and regulations for legally-appropriate informed consent vary on national, state, and local levels, but are generally based on internationally recognized pillars of ethical conduct for research on human subjects.²⁶⁻³¹

Optional vs. Required Subject Participation

Depending on the relevance of biomarker research to a clinical development program at the time of protocol development, the biomarker research may be a core required component of a trial (e.g., key to elucidating the drug mechanism of action or confirming that the drug is interacting with the target) or may be optional (e.g., to gain valuable knowledge that enhances the understanding of diseases and drugs). Informed consent for the collection of biomarker samples may be presented either in the main clinical informed consent form or as a separate informed consent form, with approaches varying somewhat across pharmaceutical companies. The relevance of biomarker research to a clinical development program may change over time as the science evolves. The samples may therefore increase in value after a protocol is developed.

Consent for Future Research Use

[figure not shown]
While it can be a challenge to specify the details of the research that will be conducted in the future, the I-PWG holds the view that future use of samples collected for exploratory biomarker research in clinical trials should be permissible when i) the research is scientifically sound, ii) participants are informed of the scope of the intended future research, even if this is broadly defined (see potential uses in Section 4 above), iii) autonomy is respected by providing the option to consent separately to future use of samples or by providing the option to terminate further use of samples upon request (consent withdrawal / sample destruction), and iv) industry standards for confidentiality protection per Good Clinical Practice guidelines are met.^{3, 31} Importantly, any research using banked samples should be consistent with the original informed consent, except where otherwise permitted by local law or regulation.

Important elements of informed consent for **future use** of samples include, but are not limited to:³⁹

The scope of research – Where the scope of the potential future research is broad, participants should be informed of the boundaries of the research. While it may not be possible to describe the exact analytical techniques that will be used, or specific molecules that will be analyzed, it is possible to clearly articulate in reasonable detail the type of research to be conducted and its purpose. Information regarding whether stored samples may be shared with other parties or utilized for commercialization purposes should also be addressed.

Withdrawal of consent / sample destruction – The informed consent form should inform participants of their right to withdraw their consent / request destruction of their samples. This should include the mechanisms for exercising that right and any limitations to exercising that right. For example, participants should be informed that it is not possible to destroy samples that have been anonymized.³ In addition, according to industry standards and regulatory guidance, participants should be informed that data already generated prior to a consent withdrawal request are to be maintained as part of the study data.³⁸

The duration of storage – The permissible duration of storage may vary according to the nature and uses of the samples and may also vary on national, state, and local levels. The intended duration of storage, including indefinite storage, should be specified.

8. Biomarker Sample Collection in Different Countries

Collection of biological samples for biomarker research is straightforward in most jurisdictions. Some countries have specific laws and regulations regarding collection, labeling, storage, export, and/or use of exploratory samples. In addition, some regulations distinguish between DNA and non-DNA samples or between samples used for diagnostic purposes and samples collected for scientific research. Processes for the collection, labeling, storage, export, and/or use of biomarker samples should always adhere to the laws and regulations of the country/region in which those samples are collected.

9. Return of Research Results to Study Participants

Policies for the return of biomarker research results to study participants who request them vary among pharmaceutical companies. There are many considerations that pharmaceutical companies weigh when determining their policy regarding the return of biomarker research results to study participants. These include:

- i) the conditions under which biomarker research results were generated (i.e., exploratory research laboratory versus accredited diagnostic laboratory)
- ii) whether the results will have an impact on the medical care of the participant or on a related person, if applicable
- iii) whether genetic counseling is recommended (for genetic results)
- iv) the ability to accurately link the result to the individual from whom the sample was collected
- v) international, national, and local guidelines, policies, legislation, and regulations regarding participants' rights to access data generated on them

Renegar *et al.* 2006 and Article 29 Data Protection Working Party (an advisory committee to the European Commission on the European Data Protection Directive) have addressed these considerations in detail in relation to pharmacogenomic research data and provided a list of documents addressing the general issue of return of research results.³⁴⁻³⁵

10. Benefits and Risks Associated with Biomarker Research

Benefits

While it may not always directly benefit the study participant who is providing the samples, biomarker research can improve overall understanding of disease and treatment of future patients receiving therapies developed from such research. Patients are now benefiting from retrospective biomarker research conducted on samples collected from clinical trials and stored for exploratory research. One example is the recent label update to the EGFR antibody drugs cetuximab (Erbix[®]) and panitumumab (Vectibix[®]) which highlights the value of *KRAS* status as a predictive biomarker for treatment of metastatic colorectal cancer with this class of drug.

The humanitarian benefit of human research is recognized by the Nuremberg Code.^{28,33} Provided that the degree of risk does not exceed that determined by the humanitarian importance of the problem to be solved, research participants should not be denied the right to contribute to the greater common good.^{28,32}

Risks

Risks associated with biomarker research are primarily related to the physical aspects of obtaining the sample and to patient privacy concerns.

Physical risks associated with biomarker sample collection in clinical trials can be characterized in two ways:
i) negligible additional risk when the biomarker sample is collected as part of a procedure conducted to support

other core trial objectives, and ii) some added risk where the sampling procedure would otherwise have not been performed as a core component of a trial. Risks are also determined by the invasiveness of the sample collection procedure.

Privacy risks are generally those associated with the inappropriate disclosure and misuse of data. Pharmaceutical companies have policies and procedures for confidentiality protection to minimize this risk for all data collected and generated in clinical trials. These may vary across companies, but are based on industry standards of confidentiality and privacy protection highlighted in the following section. Importantly, privacy risks inherent to biomarker data are no greater than other data collected in a clinical trial.

11. Privacy, Confidentiality, and Patient Rights

Maintaining the privacy of study participants and the confidentiality of information relating to them is of paramount concern to industry researchers, regulators, and patients. Good Clinical Practice (GCP), the standard adhered to in pharmaceutical clinical research, is a standard that

"...provides assurance that the data and reported results are credible and accurate, and that the rights, integrity, and confidentiality of trial subjects are protected",

where confidentiality is defined as, *"The prevention of disclosure, to other than authorized individuals, of a sponsor's proprietary information or of a subject's identity."*

This standard dictates that *"the confidentiality of records that could identify subjects should be protected, respecting the privacy and confidentiality rules in accordance with applicable regulatory requirements."*³¹

Exploratory biomarker research in pharmaceutical development is commonly conducted in research laboratories that are not accredited to perform diagnostic tests used for healthcare decision-making. Therefore, results from exploratory biomarker research usually are not appropriate for use in making decisions about a trial participant's health. In addition, exploratory research data should not be included as part of a participant's medical record accessible for use by insurance companies. Legislation and policies to protect individuals against discrimination based on genetic information continually evolve based on social, ethical, and legal considerations. Examples of such legislation include the Human Tissue Act 2004 (UK) and the Genetic Information Nondiscrimination Act (GINA) 2008 (USA).³⁶⁻³⁷

12. Where to Get More Information?

12.4 Response Evaluation Criteria in Solid Tumors (RECIST) 1.1

RECIST version 1.1* will be used in this study for assessment of tumor response. While either CT or MRI may be used utilized, as per RECIST 1.1, CT is the preferred imaging technique in this study.

* As published in the European Journal of Cancer: E.A. Eisenhauer, P. Therasse, J. Bogaerts, L.H. Schwartz, D. Sargent, R. Ford, J. Dancey, S. Arbuck, S. Gwyther, M. Mooney, L. Rubinstein, L. Shankar, L. Dodd, R. Kaplan, D. Lacombe, J. Verweij. New response evaluation criteria in solid tumours: Revised RECIST guideline (version 1.1). Eur J Cancer. 2009 Jan;45(2):228-47.

12.5 Common Terminology Criteria for Adverse Events (CTCAE) v4.0

The descriptions and grading scales found in the revised NCI Common Terminology Criteria for Adverse Events (CTCAE) version 4.0 will be utilized for adverse event reporting. (https://ctep.cancer.gov/protocolDevelopment/electronic_applications/ctc.htm)

12.6 ECOG Performance Status

GRADE	ECOG PERFORMANCE STATUS
0	Fully active, able to carry on all pre-disease performance without restriction
1	Restricted in physically strenuous activity but ambulatory and able to carry out work of a light or sedentary nature, e.g., light house work, office work
2	Ambulatory and capable of all selfcare but unable to carry out any work activities; up and about more than 50% of waking hours
3	Capable of only limited selfcare; confined to bed or chair more than 50% of waking hours
4	Completely disabled; cannot carry on any selfcare; totally confined to bed or chair
5	Dead

<http://ecog-acrin.org/resources/ecog-performance-status>

12.7 CCG Formula

$$\text{ClCr (mL/min)} = \frac{Q \times (140 - \text{age}[\text{yr}]) \times \text{ideal body weight}[\text{kg}]^*}{72 \times \text{serum creatinine [mg/dL]}}$$

Q = 0.85 for females

Q = 1.0 for males

-- OR--

$$\text{ClCr (mL/min)} = \frac{K \times (140 - \text{age}[\text{yr}]) \times \text{ideal body weight}[\text{kg}]^*}{\text{Serum creatinine [umol/L]}}$$

K = 1.0 for females

K = 1.23 for males

*Calculation of Ideal Body Weight Using the Devine Formula

Ideal body weight:

Males = 50.0 kg + (2.3 kg x each inch over 5 feet) or 50.0 kg + (0.906 kg x each cm over 152.4 cm)

Females = 45.5 kg + (2.3 kg x each inch over 5 feet) or 45.5 kg + (0.906 kg x each cm over 152.4 cm)

Example: Male, actual body weight = 90.0 kg, height = 68 inches

Ideal body weight = 50.0 + (2.3) (68-60) = 68.4 kg.

This subject's actual body weight is >30% over ideal body weight. Therefore, in this case, the subject's ideal body weight of 68.4 kg should be used in calculating estimated CrCl.

Reference

Devine, BJ. Case Number 25 Gentamicin Therapy: Clinical Pharmacology Case Studies. Drug Intelligence and Clinical Pharmacy. 1974; 8:650-655

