 - Criterion 4a is applicable only to enrollment of melanoma subjects in Parts 1, 2, and 3 of the trial design. Criterion 4b is applicable only to enrollment of melanoma subjects in Parts 1, 2, 4, and 5 of the trial design. The inclusion criterion does not apply to solid tumor subjects in Parts 4 and 5 (dose confirmation only).

Note: Local laboratory testing for BRAF mutation is acceptable provided the methodology can detect both V600E and V600K mutations.

5. For BRAF mutation-negative (wild type) subjects who have received prior therapy for metastatic or advanced melanoma, must have documented progression of at least one measurable lesion by RECIST 1.1 on imaging studies (CT or MRI).
6. Have a performance status of 0 or 1 on the Eastern Cooperative Oncology Group (ECOG) Performance Scale.
7. Have an anticipated life expectancy of at least 3 months.
8. Be able to swallow and retain oral medication and must not have any clinically significant gastrointestinal abnormalities that may alter absorption such as malabsorption syndrome or major resection of the stomach or bowels.

9. Have adequate organ function as defined in [Table 8](#) below:

Table 8 Inclusion Criteria Laboratory Parameters

System	Laboratory Value
Hematological	
Absolute neutrophil count (ANC)	≥1,500 /mcL
Platelets	≥100,000 / mcL
Hemoglobin	≥9 g/dL or ≥5.6 mmol/L
Renal	
Serum creatinine	≤1.5 X upper limit of normal (ULN)
Calculated creatinine clearance ^a	≥50 mL/min
Hepatic	
Serum total bilirubin	≤ 1.5 X ULN OR Direct bilirubin ≤ ULN for subjects with total bilirubin levels > 1.5 X ULN
AST (SGOT) and ALT (SGPT)	≤ 2.5 X ULN
Alkaline Phosphatase	If > 2.5 X ULN, then liver fraction should be ≤ 2.5 X ULN
Albumin	≥ 2.5 g/dL
Coagulation	
International Normalized Ratio (INR) or Prothrombin Time (PT)	≤1.5 X ULN unless the subject is receiving anticoagulant therapy as long as PT or aPTT is within therapeutic range of intended use of anticoagulants
Activated Partial Thromboplastin Time (aPTT)	≤1.5 X ULN unless the subject is receiving anticoagulant therapy as long as PT or aPTT is within therapeutic range of intended use of anticoagulants
a Calculate creatinine clearance using standard Cockcroft-Gault formula (Appendix 12.7). Creatinine clearance must be ≥50 mL/min to be eligible.	

10. Have provided tissue for biomarker analysis from a newly or recently-obtained biopsy (within 90 days of Study Day 1) of a tumor lesion not previously irradiated.

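### The female constant in the umol/L creatinine-clearance formula (1.0) does not match the mg/dL form (about 1.04), so a woman just above the 50 mL/min entry limit can pass in one unit and fail in the other

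*Combined protocol and SAP*

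**What the plan says.** Section 5.1.2, Table 8, footnote a, directs sites to Appendix 12.7 for calculated creatinine clearance and sets the limit: "Creatinine clearance must be ≥50 mL/min to be eligible". The calculation is a scheduled screening item in the treatment-phase flow charts (Sections 6.1.1 to 6.1.4).

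Appendix 12.7 offers two forms as alternatives. They share the same age term and the same ideal-body-weight term and differ only in the creatinine unit and the leading constants:

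- mg/dL form, with 72 in the denominator: "Q = 0.85 for females" and "Q = 1.0 for males".
- umol/L form, with no 72: "K = 1.0 for females" and "K = 1.23 for males".

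Ideal body weight comes from the Devine formula, for example "Females = 45.5 kg + (2.3 kg x each inch over 5 feet" for women. A worked example for a man then remarks: "This subject's actual body weight is >30% over ideal body weight". From that it concludes that his ideal weight should be used.

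**The concern.** Two unit forms of one formula must give the same answer for the same person. If they do not, the laboratory's reporting unit becomes an unstated part of an eligibility criterion. The trial is described as worldwide, and its renal toxicity table (Table 23) quotes creatinine in both units, so both forms should be expected in use. At stake is consistent application of one entry limit to women close to it.

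**Working it through.** **Inputs.**
- From Appendix 12.7: Q = 0.85 (female) and 1.0 (male), denominator constant 72; K = 1.0 (female) and 1.23 (male).
- From Table 23 (Section 5.6.1.1.9): 0.5 mg/dL is paired with 44 umol/L, so f = 44/0.5 = 88 umol/L per mg/dL; 2 mg/dL is paired with 177 umol/L, so f = 177/2 = 88.5.
- From Table 8: limit of 50 mL/min.

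**Step 1. Check that needs no conversion factor.** The age and weight terms are the same in both forms, so the female-to-male ratio must be the same.
- mg/dL form: 0.85/1.0 = 0.85.
- umol/L form: 1.0/1.23 = 0.813.

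The ratios differ. Holding the male constant at 1.23, the female constant should be 0.85 × 1.23 = 1.0455.

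**Step 2. Which constant is out of line.** Equating the two forms gives K = Q × f/72.
- Male: 1.0 × 88/72 = 1.222 and 1.0 × 88.5/72 = 1.229. The stated 1.23 is reproduced to within 0.1% to 0.6%.
- Female: 0.85 × 88/72 = 1.039 and 0.85 × 88.5/72 = 1.045. The stated 1.0 is not reproduced.

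Only the female umol/L constant departs from the rest. Table 23 also pairs 0.2 mg/dL with 18 umol/L (f = 90). That is coarse rounding; taken literally it gives 0.85 × 90/72 = 1.0625, which would widen the gap.

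**Step 3. Size.** The umol/L form divided by the mg/dL form, for any woman, is 1.0/K.
- f = 88: 1/1.039 = 0.963, or 3.7% lower.
- f = 88.5: 1/1.045 = 0.957, or 4.3% lower.

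The umol/L form returns exactly 50 when the mg/dL form returns 50 × 1.039 = 51.9 (f = 88) or 50 × 1.045 = 52.2 (f = 88.5). Women with an mg/dL result from 50.0 up to about 52 mL/min therefore change status.

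**Step 4. Example.** Woman aged 65, height 64 in, creatinine 0.95 mg/dL. Ideal weight = 45.5 + 2.3 × 4 = 54.7 kg.
- mg/dL form: 0.85 × 75 × 54.7/(72 × 0.95) = 50.98. Eligible.
- umol/L form, K = 1.0, f = 88: 75 × 54.7/(0.95 × 88) = 49.07. Ineligible.
- umol/L form, K = 1.0, f = 88.5: 75 × 54.7/(0.95 × 88.5) = 48.80. Ineligible.

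**Step 5. After the correction.** With K = 1.04 the same woman gives 1.04 × 49.07 = 51.0 (f = 88) or 1.04 × 48.80 = 50.8 (f = 88.5). Both forms now find her eligible.

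**The case against.** The best defence is that 1.0 is simply about 1.04 rounded to one decimal. That explains the figure but does not remove its effect: the male constant beside it carries two decimals, and the rounding moves every woman's result by about 4% at a hard limit.

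The objections on consequence carry more weight.
- The affected band is narrow, and the documents do not say how many sites report in umol/L or how many women fall in it.
- Section 7.1.5.1 allows screening procedures to be repeated and subjects to be rescreened, which softens exclusion on one borderline value.
- The current text is Amendment 6. The Part 3 final analysis is already reported (Section 5.2.5) and the Part 5 expansion has been dropped, so a change now cannot affect Part 3 enrolment.

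These points stand and keep this minor.

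A reader might go further in three ways that the documents do not support.
- *Women were wrongly excluded.* The appendix shows two forms that disagree, not that any woman was turned away in error. Inconsistent application of the limit is as far as it goes.
- *Any borderline case flips.* Near the top of the band the result depends on the conversion factor. A woman aged 60, ideal weight 55 kg, creatinine 1.0 mg/dL has 0.85 × 80 × 55/72 = 51.9 in mg/dL. In umol/L she has 80 × 55/88 = 50.0, still eligible, at f = 88, but 80 × 55/88.5 = 49.7, ineligible, at f = 88.5.
- *The choice of body weight could move the result by up to 30%.* The example's remark about being more than 30% over ideal weight (90/68.4 = 1.32) may suggest that actual weight applies otherwise. No passage says so: both formulas specify ideal weight, and the example uses it too. The remark sits oddly with a formula that always uses ideal weight, but that is a wording point and supports no magnitude.

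**Conclusion.** The inconsistency is real and can be shown from the protocol alone. The female umol/L constant should be about 1.04 (1.04 to 1.05) to match the mg/dL factor of 0.85; at 1.0 the umol/L form reads about 4% lower. The consequence is limited to women whose mg/dL result is between 50.0 and about 52 mL/min, and always in the direction of exclusion by the umol/L form. Men are unaffected. No sample size, power, alpha or endpoint figure depends on it.

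This rests on two assumptions: that the two forms are meant to be the same formula, as their presentation as alternatives indicates, and that the mg/dL factor of 0.85 is the intended one. The second is supported by the male pair and the Table 23 conversions, which leave only the female umol/L constant out of line. It is a small correction, worth making because the appendix is the operative test for a mandatory entry criterion.

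**What to change.** Reconcile the two forms in Appendix 12.7 so that they give the same result, by setting the female umol/L constant to about 1.04 to match 0.85 in the mg/dL form. At two decimals the remaining disagreement is at most about 0.5% (1.04/1.045 = 0.995 at f = 88.5; 1.04/1.039 = 1.001 at f = 88).

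In the same edit, reword the worked example so that its remark about weight more than 30% over ideal agrees with the weight term in the formula, leaving one stated weight rule. Which rule is intended is for the sponsor to state.

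The cost is one constant and one sentence. The edit can travel with any other protocol revision, subject to whatever ethics review that revision needs.
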